
VERSION NUMBER		AUTHOR	APPROVER	EFFECTIVE DATE	REVISION DESCRIPTION (INCLUDING SECTIONS REVISED)
SAP	Protocol				
					
problem in the analyses of results of interim visits when using Barnard's test, the 24-month primary time point is largely unaffected, as the amount of missing data is minimal.
 
3.Per discussion with the study leads, to evaluate biologic activity of the drops, and the potential effect of dilute atropine on accommodation, as a post hoc analysis, mean binocular near point of accommodation at 6 months was compared between treatment groups using an ANCOVA model, adjusting for baseline binocular near point of accommodation, age, iris color (brown vs. not brown), and race (East Asian vs. non-East Asian).

20

21 The primary objective of MTS1 is to determine the efficacy of daily low-dose atropine  
22 (0.01%) for slowing myopia progression over a two-year treatment period in children  
23 aged 5 to less than 13 years with myopia -1.00D to -6.00D at the time of enrollment.

24  
25 Participants are randomly assigned 2:1 to the following two treatment groups:

- 26 • Atropine Group: 0.01% atropine eyedrops administered 1 drop to each eye daily for  
27 24 months, followed by 6 months off atropine eyedrops
- 28 • Placebo Group: Placebo eyedrops administered 1 drop to each eye daily for 24  
29 months, followed by 6 months off placebo eyedrops

30  
31  
32 **1. Primary Analysis: Refractive Error at 24 Months (On-Treatment)**

33 The primary analysis will be a treatment group comparison of mean change from baseline  
34 to 24 months in spherical equivalent refractive error (SER), as measured by a masked  
35 examiner using cycloplegic autorefraction, using a longitudinal discrete time mixed  
36 model. The population-averaged method will be used to model the repeated measures on  
37 SER at 6, 12, 18, and 24-month visit. The time variable will be categorical to not impose  
38 assumptions regarding trend of SER over time. The correlations between SER  
39 measurements within person across visits will be estimated and a correlation structure  
40 will be selected accordingly. (Given that the follow-up visits are approximately equally  
41 spaced, an autoregressive covariance structure is considered likely. Other correlation  
42 structures will also be fitted, and the information criteria will be used to select the most  
43 appropriate covariance structure.) The model will include the interaction between time  

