44 and treatment group and adjust for baseline SER, age, iris color (brown vs. non-brown),  
45 and race (East Asian vs. non-East Asian), to account for potential residual confounding,  
46 and improve power for the treatment comparison. The web data entry system mandated  
47 that baseline SER, age, and iris color could not be missing at enrollment. The value  
48 ‘unknown’ will be used in the mixed model for missing race/ethnicity value.

49  
50 Given that at most a small number of participants of East Asian race are expected to have  
51 non-brown iris, there is a possibility of partial aliasing when including both race and iris  
52 color in the mixed model. If the fully-adjusted model fails to converge, or displays  
53 evidence of estimate instability, such as very large standard error associated with a  
54 partially-aliased covariate, the race and iris color variables will be combined as follows:  
55 East Asian (regardless of eye color), non-East Asian with brown eyes, non-East Asian  
56 with non-brown eyes. The number of East Asians with non-brown eye color will be  
57 tabulated and reported.

58  
59 At baseline and all follow-up visits, including the 24-month visit, the mean of the three  
60 readings from autorefraction in each eye will be calculated and the mean of both eyes for  
61 each participant will be used for the analysis. If fewer than 3 readings are available in  
62 each eye, the mean of available readings will be used for each eye to obtain the mean of  
63 both eyes for each participant. If data from only one eye is available, the mean of  
64 readings on that eye will be used for analysis.

66 The mean change from baseline to 24 months in SER in each treatment group and the  
67 treatment group difference (atropine – placebo), together with their corresponding 95%  
68 confidence intervals, will be estimated using the mixed model with maximum likelihood  
69 estimation. Maximum likelihood estimation gives unbiased estimates of treatment effect  
70 in the presence of missing outcome data, as long as the missing data is missing at random  
71 (MAR) conditional on the variables included in the analysis model. The 2-sided null  
72 hypothesis of mean treatment difference equals zero (superiority hypothesis) will be  
73 tested at an alpha level of 0.05.

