189 (East Asian vs. non-East Asian).

190

191

192 **4. Subgroup Analysis**

193 The treatment group difference for change in SER from baseline to 24 and 30 months  
194 within the following subgroups will be explored:

195

- East Asian vs. non-East Asian race

196

- Brown iris versus non-brown iris

197

- Baseline younger versus older age (based on median split)

198

- Baseline lower versus higher myopia level by SER (based on median split)

199

- Baseline age and baseline SER (4 categories based on median splits)

200

201 An estimate of the treatment effect within each subgroup and a 95% confidence interval  
202 will be obtained for each of the times, 24 and 30 months, by adding a treatment by time

203 by subgroup interaction into the primary analysis model and generating the appropriate  
204 contrasts. Each subgroup effect will be estimated separately, one subgroup per model.

205  
206 Previous studies have suggested that race and/or eye color may interact with the  
207 treatment effect of atropine. Several studies have consistently found atropine to be  
208 effective in East Asian populations and a meta-analysis has suggested that atropine might  
209 be more effective in Asian populations than in white children, although this conclusion is  
210 limited by the lack of studies in non-Asian populations. Other research has shown that  
211 atropine is rapidly taken up by melanocytes and released over time, leading to a longer  
212 time to achieve mydriasis and a prolonged mydriatic effect in heavily-pigmented eyes as  
213 atropine is released over time, potentially leading to an increased treatment effect.  
214 Conversely, if the mechanism by which atropine slows myopic progression is through  
215 local retinal effects, one might speculate that higher melanocyte density might prevent  
216 the atropine from reaching the retina, which might result in brown eyes having less  
217 treatment effect than non-brown eyes.

218  
219 Atropine might be expected to be more effective in children with lower amounts of  
220 myopia given more potential for suppression of myopia progression. Likewise, atropine  
221 might be hypothesized to have a greater treatment effect in younger than in older children  
222 given they are earlier in the course of myopic progression and have more room for  
223 potential suppression.

224  
225 For each time point, the planned subgroup analyses also will be conducted using a  

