226 continuous time longitudinal model, if linearity assumptions with time are met, to obtain  
227 p-values for the subgroup effect. Even if change in SER is not precisely linear with time,  
228 if it is monotonically decreasing, the continuous model is expected to have higher power  
229 than the discrete time primary analysis model, and will be favored over the discrete time  
230 model for obtaining p-values. The baseline factor and the baseline factor by treatment  
231 interaction will be included as terms in the model, and the 3-way subgroup, time, and  
232 treatment interaction will be used to determine whether there is a significant subgroup  
233 effect. The false discovery rate for the subgroup analyses will be controlled using the  
234 two-stage step up FDR procedure to control the overall FDR at 5%. Subgroup analyses  
235 will be interpreted with caution, particularly if the corresponding overall analysis does  
236 not demonstrate a significant treatment group difference.

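### SAP Section 4: the terms listed for the continuous-time subgroup model leave out baseline factor by time, so the 3-way test, if fitted as worded, does not isolate a difference in treatment effect

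*SAP*

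**What the plan says.** Section 4 plans two subgroup models.

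- **Estimates.** Within-subgroup effects and 95% confidence intervals at 24 and 30 months come from the discrete-time model, by adding a treatment by time "by subgroup interaction into the primary analysis model and generating the appropriate" contrasts.
- **P-values.** These come from a continuous-time model if linearity with time holds. Where change is only monotone, that model is still expected to have more power "than the discrete time primary analysis model, and will be favored over the discrete time" model. Its terms are given as "The baseline factor and the baseline factor by treatment" "interaction will be included as terms in the model, and the 3-way subgroup, time, and" treatment interaction is then used to decide whether there is a subgroup effect.

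The primary model in Section 1 is the only other place from which terms could be inherited. There, "The model will include the interaction between time" "and treatment group and adjust for baseline SER, age, iris color (brown vs. non-brown") and race. The covariates enter as adjustment terms, and none is crossed with time.

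The subgroup list includes "Baseline younger versus older age (based on median split"). Section 4 expects a larger effect in younger children "given they are earlier in the course of myopic progression and have more room for" suppression.

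**The concern.** In a model of change over time, the baseline factor by time term carries the natural course: how fast each subgroup progresses whatever the treatment. The 3-way term should then carry only the difference between subgroups in the treatment effect on slope. If baseline factor by time is absent, the 3-way term is the only one left that can absorb a subgroup difference in progression rate.

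At stake is a subgroup effect of atropine declared significant when atropine works equally well in both subgroups. The FDR procedure in Section 4 would not catch this, because it takes each p-value as a valid test of its own hypothesis. The problem would arise even if progression were exactly linear, so it is separate from the choice between a linear slope and time-point contrasts.

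**Working it through.** The SAP gives no sample size, power or error rate for this test, so there is no stated figure to reproduce.

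**Step 1: algebra, with no assumed figures.** Let S be the subgroup (0/1), A the arm (0/1) and T time. Let the true slopes show a natural subgroup difference d and a treatment effect e that is the same in both subgroups:

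| Cell | True slope | Slope allowed by listed terms (A=1 for atropine) |
|---|---|---|
| Placebo, S=0 | m | b_T |
| Placebo, S=1 | m+d | b_T |
| Atropine, S=0 | m+e | b_T + b_AT |
| Atropine, S=1 | m+e+d | b_T + b_AT + b_SAT |

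- With baseline factor by time included, the 3-way coefficient is [(m+e+d) − (m+e)] − [(m+d) − m] = 0, as it should be.
- Without it, both placebo subgroups share one slope and b_SAT = (m+e+d) − (m+e) = d.
- With placebo coded 1, the coefficient is again d, now taken from the placebo arm. The apparent direction of effect modification therefore reverses with the choice of reference arm.
- With class coding, the term has 2 df and tests whether the subgroup slopes differ in either arm.

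**Step 2: size, by formula.** From the SAP: 2:1 allocation; visits at 6, 12, 18 and 24 months; median-split subgroup. Assumed: N=180, slope SD 0.35 D/yr, residual SD 0.2 D, and d of 0.1 or 0.2 D/yr in both arms.

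- Visit times in years are 0.5, 1, 1.5 and 2, with mean 1.25. The sum of squared deviations is 2×0.75² + 2×0.25² = 1.25.
- Variance of one child's fitted slope: 0.35² + 0.2²/1.25 = 0.1225 + 0.032 = 0.1545.
- Cell sizes: 120 on atropine gives 60 per subgroup; 60 on placebo gives 30 per subgroup.
- SE of the subgroup slope difference: atropine √(0.1545×2/60) = 0.0718; placebo √(0.1545×2/30) = 0.1015.
- d=0.1: z = 1.39 (atropine=1) and 0.99 (placebo=1). The 2-df noncentrality is 1.94 + 0.97 = 2.91.
- d=0.2: z = 2.79 and 1.97. The noncentrality is 7.77 + 3.88 = 11.65.

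Rejection rates at two-sided 5%, all of them false positives:

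| Coding | d=0.1, formula | d=0.1, simulation | d=0.2, formula | d=0.2, simulation |
|---|---|---|---|---|
| 0/1, atropine=1 | 29% | 27% | 80% | 77% |
| 0/1, placebo=1 | 17% | 17% | 50% | 49% |
| Class, 2 df | 31% | 30% | 87% | 86% |
| Baseline factor by time included | 5% | about 5% | 5% | about 5% |

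**Step 3: sensitivity to N.** A simulation of 1,000 runs per setting at d=0.2 gave, across the three codings, 42-82% at N=150, 56-91% at N=200 and 70-98% at N=300. Over all settings with d from 0 to 0.3, the model with baseline factor by time rejected in 3.5-6.4% of runs. With d=0, the listed model also stayed near 5% (3.5-6.0%).

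**The case against.** The strongest reply is that the sentence is not a full model specification. It does not say that only these terms are included, and it does not name time, treatment or treatment by time either. Elsewhere the SAP names the highest-order term and leaves the rest implied: the primary model names the time by treatment interaction without a treatment main effect, and the discrete-time subgroup model names only the 3-way term. Testing a 3-way interaction given its lower-order terms is ordinary practice, and the purpose stated in Section 4 is to look for interaction with the treatment effect.

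Much of this stands. An analyst may well fit the full hierarchy, and then there is no fault. But the other unnamed terms can be taken from the primary model, and baseline factor by time cannot. The sentence also does name one two-way interaction of the baseline factor, the one with treatment, and leaves out its counterpart with time. An analyst who follows the wording gets the wrong test.

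A reader might go further and infer any of the following. The SAP does not support them.

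- **That all planned subgroup p-values are invalid.** This holds only for the model as worded, and only where subgroups progress at different rates.
- **That a false race effect is to be expected.** Nothing in the SAP says that natural progression differs by race. Even for age, the text gives a reason for a larger treatment effect; faster natural progression is plausible but not stated.
- **That the subgroup estimates or the main results are affected.** The estimates come from the discrete-time model, which under class coding can still fit every cell mean. The primary and secondary comparisons do not use this model.

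**Conclusion.** The point holds as a defect of wording with a real consequence if the wording is followed: the listed terms give a test that does not separate effect modification from natural differences in progression. The algebra needs no assumptions. The inflation, 17-30% at 0.1 D/yr and 49-86% at 0.2 D/yr against a nominal 5%, rests on the assumed N, SDs and rate difference and varies with coding, so it is illustrative.

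It is worth correcting because this model is the preferred source of subgroup p-values. The consequence is limited: the subgroup analyses are exploratory, and Section 4 already asks for caution in reading them.

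**What to change.** In Section 4, state that the continuous-time subgroup model contains time, treatment, the baseline factor and all three two-way interactions (treatment by time, baseline factor by treatment, baseline factor by time). State that the subgroup p-value is for the 3-way term given all lower-order terms, with 1 df for a two-level subgroup and 3 df for the four-category age and SER subgroup. State the same hierarchy for the discrete-time model that gives the estimates.

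The cost is one sentence and one more model term. Fewer subgroup effects may reach nominal significance, since the correct contrast has a larger standard error: under the assumptions above, √(0.0718² + 0.1015²) = 0.124 against 0.0718 for the atropine=1 coding.

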## 237 238 239 **5. Additional Analyses**

240 The overall false discovery rate for the additional analyses specified in Section 5.1 and  
241 5.2 below will be controlled at the 5% level using the two-stage step up false discovery  
242 rate (FDR) procedure.

### 243 244 **5.1. Treatment Effect Over First Year of Treatment**

245 The treatment effect on change in SER from baseline through the first year will be  
246 compared with the treatment effect on change in SER from end of first year through the  
247 second year, by constructing the appropriate contrasts in the primary analysis model.

249 **5.2.Exploratory Analyses of Additional Ocular Biometric Parameters**

250 As exploratory analyses at 24 and 30 months, change in flat corneal radius, anterior  
251 chamber depth, and lens thickness from baseline will each be compared between  
252 treatment groups using a longitudinal discrete time mixed model with maximum  
253 likelihood estimation, including the interaction between time and treatment group, and  
254 adjusting for the baseline covariates from the primary analysis model. The same  
255 strategies specified in the primary analysis (Section 1, excluding sensitivity analysis) will  
256 be used to choose the appropriate covariance structure for the model.

257  
258 At baseline and all follow-up visits, including the 12 and 24-month visits, the mean of the  
259 readings in both eyes for each participant will be used for the analysis. If data from only  
260 one eye is available, the reading on that eye will be used for analysis. The treatment  
261 group differences (atropine – placebo) and a 95% confidence interval will be estimated  
262 using the mixed model.

263  
264 **5.3.Data Tabulations**

265 The following tabulations will be performed both according to treatment group and  
266 among overall sample:

- 267 • Baseline demographics and clinical characteristics
- 268 • A flow chart accounting for all participants for all visits and phone calls
- 269 • Visit and phone contact completion rates for each follow-up visit
- 270 • Protocol deviations
- 271 • Proportion of participants needing bifocals by 24 months (i.e. during treatment)

272  
273 **5.4.Compliance**

274 Compliance with study medication will be assessed at the 6-month, 12-month, 18-month,  
275 and 24-month outcome exams. For each of these exams, the proportion of calendar days  
276 that study medication was reported used and the proportion of unused study medication  
277 ampules will be tabulated in each of the two treatment groups.

278  
279 Compliance with refractive correction will be assessed at the 6-month, 12-month, 18-  
280 month, and 24-month outcome exams. After discussion with the parent and child, study  
281 personnel will classify the proportion of time refractive error was worn will be described  
282 as excellent (76% to 100%), good (51% to 75%), fair (26% to 50%), or poor ( $\leq 25\%$ ).  
283 The distribution of refractive correction compliance will be tabulated in each of the two  
284 treatment groups.

285  
286  
287 **6. Safety Analyses**

288  
289 **6.1.Adverse Events of Eye Drops**

290 An eye drops questionnaire will be administered at randomization and at each follow-up  
291 visit. The distribution of scores on each survey item will be summarized by treatment  
292 group at the time of randomization and at each follow-up exam up until and including the  
293 24-month visit. The average of the item responses at the 24-month visit will be calculated  
294 and compared with a t-test for difference in distributions between treatment groups.

295  
296  
297  
298  
299  
300  
301  
302  
303  
304  
305  
306  
307  
308  
309  
310  
311  
312  
313  
314  
315  
316  
317  
318  
319  
320  
321  
322  
323  
324  
325  
326  
327

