					
Section 3 The overall false discovery rate (FDR) in the secondary analyses will be controlled at the 5% level using the two-stage step-up FDR procedure.
 
Section 4 1.It is specified that the subgroup analysis based on baseline age and baseline SER will be in 4 categories based on median split. 2.It is specified that an estimate of the treatment effect within each subgroup and a 95% confidence interval will be obtained for each of the times, 24 and 30 months, by adding a treatment by time by subgroup interaction into the primary analysis model and generating the appropriate contrasts. Each subgroup effect will be estimated separately, one subgroup per model. 3.The overall FDR in the subgroup analyses will be controlled at the 5% level using the two-stage step-up FDR procedure.
 
Section 5 The overall FDR in the additional analyses will be controlled at the 5% level using the two-stage step-up FDR procedure.
 
Section 6 1.In the previous version, it was specified that the average of the item responses at the 6-month visit would be calculated and compared using a Wilcoxon Rank Sum test for difference between the treatment groups. In the current version, it has been updated to comparing the average of the item responses at 24-month visit using a t-test to be consistent with the protocol. 2.The adjustment of FDR has been removed given that there is only one average score for the questionnaire.
 
Section 7 1.Given that by the time sufficient data allowing for an analysis of efficacy or futility for the primary outcome would be possible, all or most subjects are expected to be within 1 year of completing the primary outcome, no formal statistical interim monitoring is proposed. 2.It has been added that the tabulated safety and efficacy data will be reviewed by the PEDIG Data and Safety Monitoring Committee at its biannual meetings,

VERSION NUMBER		AUTHOR	APPROVER	EFFECTIVE DATE	REVISION DESCRIPTION (INCLUDING SECTIONS REVISED)
SAP	Protocol				
					and if any unexpected safety or other issues arise, they can recommend to stop the study at any time.

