### 152 **3.1. Proportion of Participants with Progression $\geq 0.5D$ , $1D$ , and $2D$**

153 The proportion of participants with progression  $\geq 0.5D$ ,  $\geq 1D$ , and  $\geq 2D$  from baseline  
154 to 12, 24, and 30 months in each treatment group will be tabulated. The proportions will  
155 be compared between treatment groups using Barnard's test.  
156  
157

158

159

160 **3.2.Change in Axial Length at 12 and 24 Months (On Treatment)**

161 Axial length will be reported as the distributions of baseline length, 12-month length, 24-  
162 month length, and change in axial length from baseline to 12 and 24 months. A treatment  
163 group comparison of the change in axial length from baseline to 12 months and 24  
164 months will be performed using a longitudinal discrete time mixed model with maximum  
165 likelihood estimation, which allows for interaction between time and treatment group,  
166 and adjusts for the same baseline covariates as the primary analysis. The same strategies  
167 specified in the primary analysis (Section 1, excluding sensitivity analysis) will be used  
168 to choose the appropriate covariance structure for the model.

169

170 At baseline and all follow-up visits, including the 12 and 24-month visits, the mean of the  
171 axial length readings in both eyes for each participant will be used for the analysis. If data  
172 from only one eye is available, the reading on that eye will be used for analysis. The  
173 treatment group differences (atropine – placebo) and a 95% confidence interval will be  
174 estimated using the mixed model.

175

176 **3.3.Change in Axial Length at 30 Months (Off Treatment)**

177 The same approach defined in Section 3.4 will be used to conduct a treatment group  
178 comparison of the change in axial length from baseline to 30 months.

179

180 **3.4.Refractive Error at 12 Months (On Treatment)**

181 The primary analysis specified in Section 1 (excluding the sensitivity analysis) will be  
182 used to obtain a treatment group comparison of change from baseline to 12-months in  
183 SER, as measured by a masked examiner using cycloplegic autorefraction.

184

185 **3.5.Near Accommodation at 6 Months**

186 As a post hoc analysis, mean binocular near point of accommodation at 6 months will be  
187 compared between treatment groups using an ANCOVA model, adjusting for baseline  
188 binocular near point of accommodation, age, iris color (brown vs. not brown), and race  

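### Section 6.1 tests the 24-month eye-drop score with an unadjusted t-test and leaves the randomization score unused; adjusting for it could sharpen the comparison, by an amount the SAP does not let one fix

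*SAP*

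**What the plan says.** Section 6.1 sets the timing: "An eye drops questionnaire will be administered at randomization and at each follow-up" visit. Item scores are to be summarized by "group at the time of randomization and at each follow-up exam up until and including the" 24-month visit. One between-group test follows. The item responses at 24 months are averaged "and compared with a t-test for difference in distributions between treatment groups". No covariate is named. (A t-test compares means, so the reference to distributions is loose wording.)

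The Revision History entry for SAP 2.0, Section 6, explains where the test came from. A 6-month Wilcoxon comparison was replaced: "it has been updated to comparing the average of the item responses at 24-month visit using a t-test to be consistent with the protocol".

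Elsewhere the plan does adjust an outcome for its own baseline. The primary model in Section 1 includes baseline SER, in part to account for residual confounding "and improve power for the treatment comparison". In Section 3.5 the near point of accommodation is "compared between treatment groups using an ANCOVA model, adjusting for baseline" near point, among other covariates.

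**The concern.** The 24-month comparison is the only between-group test of the questionnaire in the plan, and a baseline value of the same score will be in the database. If that value predicts the 24-month score, leaving it out costs precision. A chance difference between groups at randomization would also carry through, in part, to the 24-month comparison. The group summaries at randomization would show such a difference but would not remove it from the test. If the two scores are unrelated, nothing is lost by ignoring the first.

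Two related points are smaller:

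- **Biometry.** Sections 3.2 and 5.2, read literally, analyse change in each biometric measure with the covariates of the primary model. Those include baseline SER but not the measure's own baseline.
- **Cross-reference.** Section 3.3 bases the 30-month axial length analysis on Section 3.4, which is 12-month SER. Section 3.2 is the axial length section.

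**Working it through.** **Inputs.** From the SAP: the questionnaire is given at randomization (6.1), the test has no covariate (6.1), and allocation is 2:1 (introduction). The SAP gives no correlation, standard deviation, expected difference or number of participants for this score, so there is no stated figure to reproduce. Assumed below: the within-group correlation rho between the randomization and 24-month scores (0 to 0.5), the number analysed N (100 to 300), and the share of missing randomization scores (10%). It is also assumed that the randomization questionnaire precedes study drops, which the SAP does not say outright.

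**Precision.** In large samples Var(ANCOVA)/Var(t-test) = 1 − rho². The standard error (SE) falls by 1 − √(1 − rho²), and the equivalent gain in participants is 1/(1 − rho²) − 1. The last column takes an unadjusted power of 80% (assumed, two-sided 5%) and gives Φ((1.960 + 0.842)/√(1 − rho²) − 1.960).

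| rho | variance ratio | SE falls by | equivalent extra participants | 80% power becomes |
|---|---|---|---|---|
| 0 | 1.00 | 0% | 0% | 80.0% |
| 0.2 | 0.96 | 2.0% | 4% | 81.6% |
| 0.3 | 0.91 | 4.6% | 10% | 83.6% |
| 0.5 | 0.75 | 13.4% | 33% | 89.9% |

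**Cost of the covariate.** The variance is multiplied by about 1 + 1/(N − 4).

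- N = 100: 1 + 1/96 = 1.0104, so the SE rises by 0.52%.
- N = 300: 1 + 1/296 = 1.0034, so the SE rises by 0.17%.

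Break-even is where (1 − rho²)(1 + 1/(N − 4)) = 1, that is rho = √(1/(N − 3)). This gives 0.102 at N = 100 and 0.058 at N = 300. Below that, adjusting loses slightly.

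**Chance imbalance at randomization.** Let z be the baseline difference in SE units. With no treatment effect, the unadjusted statistic given z is distributed N(rho·z, 1 − rho²), and the test rejects when its absolute value exceeds 1.96.

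| rho | shift at z = 1.96 | rejection at z = 1.96 | rejection at z = 1 |
|---|---|---|---|
| 0 | 0 SE | 5.0% | 5.0% |
| 0.2 | 0.39 SE | 6.3% | 5.0% |
| 0.3 | 0.59 SE | 7.9% | 5.0% |
| 0.5 | 0.98 SE | 12.9% | 4.8% |

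Over all randomizations the t-test rejects 5% of the time.

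**Missing randomization scores.** Section 1 says only "that baseline SER, age, and iris color could not be missing at enrollment"; it gives no such guarantee for the questionnaire. Suppose a fraction m is missing completely at random.

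- Complete-case ANCOVA has variance ratio (1 − rho²)/(1 − m), so it is worse than the t-test once m exceeds rho²: 4, 9 and 25% at rho 0.2, 0.3 and 0.5.
- Imputing the pooled mean gives 1 − (1 − m)rho². At m = 10% this is 0.964, 0.919 and 0.775, so the SE still falls by 1.8, 4.1 and 12.0%.

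**Simulation check** (2:1 allocation, assumed N = 180, 20,000 runs per setting). The SE ratios were 1.002, 0.981, 0.956 and 0.868 at rho 0, 0.2, 0.3 and 0.5 with no missing scores. They were 1.002, 0.986, 0.960 and 0.886 with 10% missing and mean-imputed. Type I error was 4.8 to 5.3% for both tests.

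**Biometry.** With equal standard deviations at both times, adding the outcome's own baseline to an analysis of change gives a variance ratio of (1 − rho²)/(2 − 2rho) = (1 + rho)/2. At assumed rho 0.90 this is 0.95 (SE 2.5% lower); at 0.98 it is 0.99 (SE 0.5% lower).

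**The case against.** The best counter-argument is that nothing here is wrong. The t-test is valid, holds its 5% level over all randomizations and was chosen on purpose to match a protocol that is not at hand. Making ANCOVA the main test would depart from that. All of this stands, and it is why the point is only one to consider.

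The size is also unknown. The items are not described in Section 6.1, and the randomization score is 24 months away from the outcome, so a weak correlation is quite possible. The most striking figure, 12.9%, needs both rho = 0.5 and a 1-in-20 imbalance. That is fair too. The case for adjusting is that the possible loss is about half a percent in SE at most for N of 100 or more, while a moderate correlation brings a useful gain.

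Other planned tests, such as Barnard's test in Sections 3.1 and 6.2, also have no covariates, and Section 3.5 is labelled post hoc. The plan is therefore not uniform in adjusting for baseline. Still, the reason given for the t-test explains where it came from and not why the baseline score goes unused.

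Timing is the most practical objection. SAP 2.1 is dated November 2022, Section 7 expected all 24-month data by December 2021, and the Revision History already describes 24-month missingness. It also reports the accommodation comparison in the past tense. Some group results may therefore have been seen, although the document does not say whether questionnaire results were. If they were, only a supporting ANCOVA is defensible.

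For biometry, baseline SER and age already in the models could absorb part of the 0.5 to 2.5%.

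**Conclusion.** The concern holds as a low-severity point. Section 6.1 leaves unused a baseline score that the trial collects, in the plan's only between-group test of the questionnaire. Adjusting lowers the SE by nothing at rho = 0 and by 13.4% at rho = 0.5, before the small covariate cost. It also removes the predictable part of any chance baseline difference. Every correlation, sample size and missing fraction used is an assumption, and the SAP does not allow the range to be narrowed. The result further depends on the randomization questionnaire preceding study drops. Confidence is medium. The t-test gives no bias, and the primary SER analysis is unaffected.

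The biometry point is minor. The Section 3.3 cross-reference is a plain editorial error.

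**What to change.** **Section 6.1.** Compare the 24-month mean item score by ANCOVA on treatment and the randomization mean item score. Impute a missing randomization score with the mean over both groups pooled, so that nobody with a 24-month score is dropped. Keep the protocol-aligned t-test as a supporting analysis and record the departure with its reason, as SAP 2.1 does for its other changes. If questionnaire results by group have already been seen, reverse the order: the t-test stays main and the ANCOVA is supporting.

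**Sections 3.2, 3.3 and 5.2.** Add each biometric outcome's own baseline to the covariates.

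**Section 3.3.** Change the reference from Section 3.4 to Section 3.2.

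**Cost.** No new data are needed. For 6.1 the change takes one degree of freedom, a one-line rule for missing randomization scores and a documented departure from the protocol-aligned test. The main drawback is that it comes late.
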